4.1.3 Method of assigning subjects to treatment groups

Part 1 (MRD part):

At Visit 2 (Day 1) eligible subjects will be randomized to treatment groups active or placebo for the current dose level under investigation in a 4:1 ratio. The assignment will occur in a blinded fashion via Interactive Response Technology (IRT). To facilitate the use of the IRT, the investigator will receive all necessary instructions.

Part 2 (cross-over part):

At Visit 2 (Day 1) of the first period eligible CF subjects will be randomized to treatment sequences active-placebo/placebo-active in a 1:1 ratio. The assignment will occur in a blinded fashion via Interactive Response Technology (IRT). To facilitate the use of the IRT, the investigator will receive all necessary instructions.

4.1.4 Drug assignment and administration of doses for each subject

The trial will be divided into two parts:

1. multiple rising dose (Healthy volunteers)
2. multiple single dose (CF subjects)

For both parts of the study the treatment phase includes a multiple-dose phase starting on Day 1 in the morning and subjects will receive medication twice daily for:

- 6 days (Day 1-6) in healthy volunteers, with a single dose administration on Day 7
- 13 days (Day 1-13) in CF subjects in a cross-over design, with a single dose administration on Day 14

For CF subjects, a second treatment phase will follow a washout period of at least 30 days. (cf. Table 4.1.4: 1 and [Table 4.1.4: 2](#) for treatments and posology overview)

Generally medication intake will be at the same time every day during the entire study to ensure a dose interval of 12 hours, respectively. The same study medication will be used during in-house confinement and outpatient periods.

Table 4.1.4: 1 Treatment overview healthy volunteers

| Treatment | Formulation, dose regimen | Route of administration | Number of actuations per single administration | Unit strength [µg] | Total dose per administration [µg] | Posology distribution over the treatment period |
|-----------|--|-------------------------|--|--------------------|------------------------------------|---|
| 1 | Inhalation solution, 13 administrations 12 hours apart | Inhalation | 1 | 100 | 100 | Day 1 to Day 6 a.m./ p.m. and Day 7 a.m. |

Table 4.1.4: 1

Treatment overview healthy volunteers (cont.)

| Treatment | Formulation, dose regimen | Route of administration | Number of actuations per single administration | Unit strength [µg] | Total dose per administration [µg] | Posology distribution over the treatment period |
|-----------|--|-------------------------|--|--------------------|------------------------------------|---|
| 2 | Inhalation solution, 13 administrations 12 hours apart | Inhalation | 4 | 100 | 400 | Day 1 to Day 6 a.m./ p.m. and Day 7 a.m. |
| 3 | Inhalation solution, 13 administrations 12 hours apart | Inhalation | 4 | 300 | 1200 | Day 1 to Day 6 a.m./ p.m. and Day 7 a.m. |
| 4 | Inhalation solution, 13 administrations 12 hours apart | Inhalation | 6 | 300 | 1800 | Day 1 to Day 6 a.m./ p.m. and Day 7 a.m. |
| Placebo* | Inhalation solution, 13 administrations 12 hours apart | Inhalation | Matching active treatment | - | - | Day 1 to Day 6 a.m./ p.m. and Day 7 a.m. |

* Subjects receiving placebo are equally distributed across dose groups

Table 4.1.4: 2

Treatment overview CF

| Treatment | Formulation, dose regimen | Route of administration | Number of actuations per single administration | Unit strength [µg] | Total dose per Administration [µg] | Posology distribution over the treatment period |
|-----------|---|-------------------------|--|--------------------|------------------------------------|---|
| 1 | Inhalation solution, 27 administrations ** 12 hours apart | Inhalation | 2 | 300 | 600 | Day 1 to Day 13 a.m./ p.m. and Day 14 a.m. |
| Placebo* | Inhalation solution, 27 administrations 12 hours apart | Inhalation | Matching active treatment | - | - | Day 1 to Day 13 a.m./ p.m. and Day 14 a.m. |

* Each subject will receive active and placebo

** Theoretical number of administrations when no time windows applied

Each newly assembled RESPIMAT Inhaler has to be primed by qualified, trained, unblinded study personnel, e.g. pharmacist at the trial site under the responsibility of the investigator, who is not involved in the conduct of the trial. Except those devices used for training, priming should NOT take place in the same room where the subject is inhaling trial medication or PK sample preparation. The inhaler should be primed by actuating it until an aerosol is visible plus three additional actuations. For detailed priming instructions please refer to the RESPIMAT Inhaler handling instructions in [Appendix 10.1](#).

Both the study drug as well as the placebo treatment (depending on randomisation) will be inhaled with the RESPIMAT in a sitting or standing position under supervision of the investigating physician or an authorised designee (see [section 4.3](#)). Inhalation of study drug should NOT take place in the same room where the blood samples are taken, to prevent contamination of samples from airborne drug. If more than one actuation is needed, planned time 0:00h will always be the first actuation. If more than one actuation will be needed, the duration from first to last actuation will be recorded. After study drug inhalation, subjects will drink 250 mL of water.

The so-called four-eye principle (two-person rule) should be applied for administration of trial medication and – if applicable – its preparation (e.g. assembling of device), if correct dosage cannot be ensured otherwise.

For restrictions with regard to diet see [section 4.2.2.3](#).

4.1.5 Blinding and procedures for unblinding

4.1.5.1 Blinding

Patients, Investigators and everyone involved in trial conduct or analysis or with any other interest in this double-blind trial will remain blinded with regard to the randomised treatment assignments until after database lock. According to the rising dose design, the current dose level will be known to subjects and investigators. At the trial site, access to the randomisation schedule is restricted to unblinded pharmacists.

The randomization code will be kept secret by Clinical Trial Support up to database lock. Access to the codes will be controlled and documented by a signed confidentiality statement, which will be stored in the TMF.

The randomization codes will be provided to bioanalytics prior to last patient out to allow them to exclude PK samples taken from placebo subjects from the bioanalytical analyses.

The Trial Bioanalyst will sign a confirmation that the codes will be treated confidentially and that all unblinding information is restricted to the laboratory staff involved in sample analysis.

In addition, the trial pharmacometrist may receive the randomisation codes of part 1 of the trial prior to official unblinding to carry out analyses to guide further internal decision making. He or she will confirm in writing that the codes will be treated confidentially. The unblinded results are not to be presented prior to official unblinding of the trial.

In addition, the trial pharmacokineticist may receive the randomisation codes of part 1 of the trial prior to official unblinding to perform preliminary PK analysis. He or she will confirm in writing that the codes will be treated confidentially. The unblinded results are not to be presented prior to official unblinding of the trial.

Within the ECG laboratory, the staff involved with interval measurements and assessments will be blinded with respect to the treatment and also with regard to the recording date and time as well as time the points of the ECGs. The interval measurements for a given subject

will be performed in a random and blinded sequence by a single technician. No more than two different blinded readers will evaluate the ECGs of the study.

If an interim safety analysis of ECG data is required, a part of the staff of the ECG laboratory may be unblinded. This part of the staff is strictly separated from those parts of the staff, which is involved with interval measurements and assessments of single ECGs (blinded).

After completion of part 1 with HV an interim database lock will be made. After this the data of HV will be unblinded. The objective of the trial especially part 2 is not expected to be affected by this as part 1 with HV will be completed and the analysis will have no impact on the conduct (in the sense of randomisation, blinding and analyses of primary endpoint) of the second part.

After completion of part 2 the final database lock of the trial will occur and the trial will be fully unblinded.

4.1.5.2 Unblinding and breaking the code

Emergency unblinding will be available to the Investigator / Pharmacist / investigational drug storage manager via IRT. It must only be used in an emergency situation when the identity of the trial drug must be known to the Investigator in order to provide appropriate medical treatment or otherwise assure safety of trial subjects or in order to make decisions on dose escalation in case of stopping criteria being triggered. The reason for unblinding must be documented in the source documents and/or appropriate CRF page along with the date of when the code was broken.

Due to the requirements to report Suspected Unexpected Serious Adverse Reactions (SUSARs), it may be necessary for a representative from Boehringer Ingelheim's Pharmacovigilance group to access the randomisation code for individual subjects during trial conduct. The access to the code will only be given to authorised Pharmacovigilance representatives and not be shared further.

4.1.6 Packaging, labelling, and re-supply

The investigational products will be provided by BI or a designated CRO. They will be packaged and labelled in accordance with the principles of Good Manufacturing Practice (GMP). Re-supply to the sites will be managed via an IRT system, which will also monitor expiry dates of supplies available at the sites.

For details of packaging and the description of the label, refer to the ISF.

4.1.7 Storage conditions

Drug supplies will be kept in their original packaging and in a secure limited access storage area according to the recommended storage conditions on the medication label. A temperature log must be maintained for documentation.

If the storage conditions are found to be outside the specified range, the local clinical monitor (as provided in the list of contacts) must be contacted immediately.

4.1.8 Drug accountability

The Investigator, Pharmacist and/or investigational drug storage manager will receive the investigational drugs delivered by the sponsor when the following requirements are fulfilled:

- Approval of the trial protocol by the IRB / ethics committee
- Availability of a signed and dated clinical trial contract between the sponsor and the head of the investigational site,
- Approval/notification of the regulatory authority, e.g. competent authority,
- Availability of the curriculum vitae of the principal Investigator,
- Availability of a signed and dated clinical trial protocol
- Availability of the proof of a medical license for the principal Investigator

The Investigator, Pharmacist and/or investigational drug storage manager must maintain records of the product's delivery to the trial site, the inventory at the site, the use by each subject, and the return to the sponsor or warehouse / drug distribution centre or alternative disposal of unused products. If applicable, the sponsor or warehouse / drug distribution centre will maintain records of the disposal.

These records will include dates, quantities, batch / serial numbers, expiry ('use- by') dates, and the unique code numbers assigned to the investigational product and trial subjects. The Investigator, Pharmacist and/or investigational drug storage manager will maintain records that document adequately that the subjects were provided the doses specified by the CTP and reconcile all investigational products received from the sponsor. At the time of return to the sponsor, the Investigator, Pharmacist and/or investigational drug storage manager must verify that all unused or partially used drug supplies have been returned by the clinical trial subject and that no remaining supplies are in the Investigator's possession.

4.2 OTHER TREATMENTS, EMERGENCY PROCEDURES, RESTRICTIONS

4.2.1 Other treatments and emergency procedures

For healthy subjects, no special emergency procedures are to be followed. However, in case of adverse events in need of treatment (e.g. treatment of hyperkalaemia), the investigator can authorise any required therapy. In those cases, subjects will be treated as necessary and, if required, kept under supervision at the trial site or transferred to a hospital until all medical evaluation results have returned to an acceptable level, same holds true for patients.

4.2.1.1 Rescue medication

Administration of PRN (Pro re nata (as occasion requires)) inhaled short acting β -adrenergics, inhaled short acting anticholinergics or combinations of both can occur at any time during the trial as deemed necessary by the subject or the investigator. However, the medication restrictions prior to lung function testing (please refer to [section 4.2.2.2](#)) must be observed as long as this is compatible with the safety of the subject. Otherwise there are no special emergency procedures to be followed.

During the whole course of the trial the site will be responsible for providing open-label

salbutamol/albuterol and / or atrovent HFA MDI to be used as rescue medication for all CF subjects at screening after they have signed their informed Consent.

Regarding the use of salbutamol for post-bronchodilator spirometry measurement please refer to [Section 5.3.6.](#)

If rescue medication is administered during clinic visits, the 24-hour clock time of rescue medication, total number of inhalations of salbutamol used, visit number, date and the name, route and dosage of any additional rescue medication will be recorded on the Rescue Medication eCRF page.

The use of rescue medication during all visits with laboratory sampling does not necessitate discontinuation of the visit. The subject should remain in the clinic in order to complete the blood sampling.

4.2.2 Restrictions

4.2.2.1 Restrictions regarding concomitant treatment

Medications causing alterations in serum electrolytes should not be administered during the study (a list of common medications effecting serum electrolyte balance is included in [Table 4.2.2.1: 1](#)). All concomitant medications must be assessed by the investigator for potential effects on serum electrolytes based on the summary of product characteristics (SPC), if applicable. Specific questions of eligibility based on this criterion should be clarified by the clinical monitor prior to inclusion. Medications not included in Table 4.2.2.1:1 may be administered at the discretion of the investigator e.g. paracetamol.

In case of adverse events in need of treatment, symptomatic therapy will be permitted as considered appropriate by the investigator. All concomitant and/or rescue therapies will be recorded (including time of intake on study days, except for salbutamol or atrovent rescue medication) on the appropriate pages of the CRF.

In addition, please note [Section 4.2.2.2](#) regarding restrictions prior to forced spirometry and [Section 4.2.2.3](#) regarding restrictions on diet and life style.

Part 1 (MRD part)

Healthy volunteers

In principle, no concomitant therapy is allowed. All concomitant or rescue therapies will be recorded (including time of intake on study days) on the appropriate pages of the CRF. Hormonal contraception must be used in WOCBP ([section 10.7](#)).

Part 2 (cross-over part)

Cystic Fibrosis

Table 4.2.2.1:1 provides an overview of permitted and restricted medications.

Table 4.2.2.1:1 Permitted and restricted medications

| Class | Permission / Restriction and explanation |
|--|---|
| Hormonal contraceptives | Permitted prior screening visit (Visit 1) and during the trial. |
| Pulmozyme® | Permitted provided that Pulmozyme has been stabilized at least 6 weeks prior to randomisation (Day 1) and will continue to be used during the trial in a stable manner. |
| Intravenous / oral antibiotics | Not permitted within 4 weeks of screening and during each treatment period when prescribed for exacerbation or acute infection. Continued stable therapy is permitted if given at that dose for at least 2 months prior to the screening visit (Visit 1) and will continue to be used during the trial in a stable manner. |
| Inhaled antibiotics | Permitted provided that antibiotics are started within 2 weeks prior to randomisation (Day 1) and will continue to be used during both treatment periods (including washout period), or are started within 2 weeks prior to randomisation and re-started within 2 weeks prior to treatment period 2 (Visit 3). |
| Ivacaftor | Not permitted 6 weeks prior screening visit (Visit 1) and during the trial. |
| Lumacaftor | Not permitted 6 weeks prior screening visit (Visit 1) and during the trial. |
| Mucolytics including inhaled hypertonic saline, Inhaled or oral N-acetylcysteine, or inhaled glutathione | Not permitted 2 weeks prior randomization (Day 1) and during the trial. |
| Inhaled corticosteroids | Permitted provided that inhaled corticosteroids have been stabilized at least 6 weeks prior to randomization (Day 1) and will continue to be used during the trial in a stable manner (including combinations containing β -adrenergics). |
| Systemic corticosteroids | Not permitted 6 weeks prior screening visit (Visit 1) and during the trial. |
| Short acting inhaled β -adrenergics | Not permitted except for supplied rescue medication. Regarding restrictions for forced spirometry bronchodilators see Section 4.2.2.2 . |
| Long acting inhaled β -adrenergics (mono-product or combined) | Permitted provided that inhaled long-acting anticholinergics have been stabilized at least 6 weeks prior to randomization (Visit 2) and will continue to be used during the trial in a stable manner. Regarding restrictions for forced spirometry bronchodilators see Section 4.2.2.2 . |
| Antihistamines | Permitted if prescribed for non-asthma condition |

Table 4.2.2.1:1 Permitted and restricted medications (cont.)

| Class | Permission / Restriction and explanation |
|---|---|
| Investigational drugs | Not permitted , see exclusion criterion number 17 |
| Medications that may lead to alterations in serum electrolytes (particularly potassium) including but not limited diuretics* angiotensin convertase/ angiotensin receptor inhibitors**, nonsteroidal anti-inflammatory drugs (NSAIDs)***, cyclosporine or tacrolimus, Pentamidine, Trimethoprim- sulfamethoxazole, Heparin, Ketoconazole and Metyrapone | Not permitted 4 weeks prior screening visit (Visit 1) and during the trial |

*includes frusemide, spironolactone, amiloride

** includes Captopril, Zofenopril, enalapril, ramipril, Quinapril, Perindopril, Lisinopril, Benazepril, Imidapril Trandolapril, Fosinopril, Cilazapril;

*** includes ibuprofen, diclofenac, naproxen, celecoxib, mefenamic acid, etoricoxib, indomethacin, aspirin (doses > 600 mg)

4.2.2.2 Medication restrictions for all lung function testing

CF subjects

Throughout the study and post treatment period including end of study visit usual background medications and trial medication should not be taken before the morning pre-dose pulmonary function testing (forced spirometry) ([Flow Chart II](#)). An 8-hour minimum washout period for inhaled short-acting bronchodilators (such as salbutamol and ipratropium) must be maintained.

On visits with several spirometry (Day 1 and Day 14), background therapy may be given after the 30 min spirometry post BI 443651 administration.

For all subjects, even if subjects violated restrictions, as a general rule, scheduled procedures (after randomization) should neither be postponed nor skipped. Regarding diet and lifestyle restrictions for forced spirometry testing please refer to Section 4.2.2.3.

4.2.2.3 Restrictions on diet and life style

Diet and lifestyle restrictions before and after administration of trial medication:

While admitted to the trial site the subjects are restricted from consuming any other foods or drinks than those provided by the staff. Standardised meals will be served at the time points described in [Flow Chart I](#) & [Flow Chart II](#).

Day 1, Day 7 and Day 14

While admitted to site on Day 1, Day 7 and Day 14, from 1 hour before drug intake until lunch, water intake and meals are restricted as per [Flow Chart I](#) & [Flow Chart II](#). From lunch onwards (on Day 1, Day 7 and Day 14), for healthy volunteers only, water intake must be up to an additional 750 mL (maximum 1,500 mL) until 1 hour prior to the evening drug administration.

The total amount of liquid intake will be documented.

For all subjects while in the unit, standardised meals will be served at the time points described in respective flowcharts. A snack is allowed (if completed) 1 hour prior to the morning dose, or started 30 minutes after the evening dose, post-body plethysmography (healthy volunteers only), if required. Use of additional table salt is not allowed during in-house confinement at the trial site.

On all other days (excl. Day 1, Day 7 and Day 14), no time restrictions will occur to meals outside of 07:00 to 20:00.

Grapefruits, Seville oranges and their juices should be avoided 7 days before and until the last PK timepoint. Excess of dried fruits (defined at > 1 standard adult portion per day) and dietary supplements containing high level of sodium and potassium should also be avoided during the trial. All non-prescribed supplements should be avoided.

For HV subject alcoholic beverages are not permitted from 48 hours prior to:

- screening
- study drug administration at Day 1, until after safety laboratory tests at Day 12.
- end of study visit

For CF subjects excess of alcoholic beverages are not permitted 48 hours prior to:

- screening
- each treatment period (Visit 2 & 3) at Day 1, until after safety laboratory tests at Day 14.
- end of study visit

Intake of methylxanthine-containing drinks or foods (coffee*, tea, cola*, energy drinks*, chocolate, etc.) are not allowed during in-house confinement and 8 hours prior to the morning of in-clinic appointments with pulmonary function tests.

*Decaffeinated beverages are allowed.

Subjects will have to adhere to restrictions resulting from ATS/ERS guidelines ([P05-12782](#)) for conduct of correct pulmonary function testing.

Excessive strenuous physical activities should be avoided starting from 72 hours prior to study drug administration and until the end-of-study examination.

Diet and lifestyle restrictions for lung function testing

The subject must refrain from strenuous activity for at least 24 hours prior to lung function testing (forced spirometry, body plethysmography). Subjects should

also avoid cold temperatures, environmental smoke, dust or areas with strong odours (e.g. perfumes). Coffee, tea, chocolate, cola and other caffeine-containing beverages and foods, and ice-cold beverages are not allowed at least 8 hours prior to and during the pulmonary function testing period at site visits. Decaffeinated beverages are acceptable.

4.2.2.4 Restrictions regarding women of childbearing potential

WOCBP must use the highly effective methods of contraception as described in the subject information.

4.3 TREATMENT COMPLIANCE

Each subject will be trained in the correct use of the Respimat® inhaler using the training Respimat® inhaler with inserted placebo cartridge. Please refer to [section 10.1](#).

Patients will be asked to return inhalation aerosols and devices (used and unused) to the study site. The trial medication adherence should be reviewed by the investigator and recorded on the appropriate drug accountability forms.

Compliance whilst in clinic will be assured by administration of all study medication under supervision of the investigating physician or a designee.

CF subjects will be reminded to administer drug during a phone call from site (morning and evening). The AM3® device will alarm to remind the patient to take drug. Drug administration (morning and evening) will be captured by site staff directly (whilst in clinic) or via telephone (whilst ex-clinic).

The measured plasma concentrations will provide additional information about compliance.

Estimating Compliance to trial medication

Compliance for Healthy Volunteers will be observed and recorded by site staff at the trial site. Compliance for CF subjects will be estimated using the records by site staff at the trial site (dosing in-clinic) and telephone calls to subjects (dosing at home). The acceptable medication compliance should have an overall value in the range from 80% to 120%. If the compliance is less than 80% or greater than 120%, the patient needs to be retrained. Randomised patients should not be discontinued for a lack of compliance without prior discussion with the clinical monitor.

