- 13) Unsupervised Pulmonary Function (FEV₁, PEF) with AM3® device
- 14) Phone call to be made twice a day, ideally at the time of study drug administration ([see section 5.3.6](#)). During the afternoon or evening calls, AEs should be collected in line with a morning call
- 15) Allocation to treatment may be performed at any time following enrolment but must be completed prior to first drug administration. Randomisation not required for CF subjects undergoing second treatment period
- 16) AEs and concomitant therapies will be recorded throughout the trial, but will be specifically asked for at the time points indicated in the [Flow Chart II](#) above including during phone calls when patients are ex clinic.
- 17) Respimat device and AM3® device training initially, then instruction (if required).
- 18) Systolic and diastolic blood pressures (BP) as well as pulse rate (PR) will be measured by a blood pressure monitor at the times indicated in the Flow Chart II, after subjects have rested for at least 5 min in a supine position.
- 19) Includes, urine pregnancy test for females at Screening, Day 1, Day 7, Day 14 and Day 30. Serum pregnancy test at Day -5 to -3, and e.o.s. visit.
- 20) To be measured on home based spirometer (AM3®), prior to drug administration.
- 21) Baseline ECG (Day 1) must be in triplicate. All other ECGs to be single.
- 22) Urine drug screen and alcohol breath test to be performed at both screening and Pre-dose Day 1.,
- 24) Serum electrolytes to be collected using local laboratory values in addition to central laboratory values.
- 25) Planned time is required for technical reasons and the actual dates and times could be between Day -7 to -3.

TABLE OF CONTENTS

| | |
|---|-----------|
| CLINICAL TRIAL PROTOCOL..... | 1 |
| TITLE PAGE | 1 |
| CLINICAL TRIAL PROTOCOL SYNOPSIS | 2 |
| FLOW CHART I – HEALTHY VOLUNTEERS | 5 |
| FLOW CHART II – CF SUBJECTS..... | 8 |
| TABLE OF CONTENTS | 11 |
| ABBREVIATIONS..... | 15 |
| 1. INTRODUCTION..... | 17 |
| 1.1 MEDICAL BACKGROUND | 17 |
| 1.2 DRUG PROFILE | 18 |
| 1.2.1 Nonclinical pharmacology..... | 18 |
| 1.2.2 Safety pharmacology..... | 19 |
| 1.2.3 Toxicology | 19 |
| 1.2.5 Drug product | 20 |
| 1.2.6 Clinical studies and experience in humans | 20 |
| 2. RATIONALE, OBJECTIVES, AND BENEFIT - RISK ASSESSMENT | 22 |
| 2.1 RATIONALE FOR PERFORMING THE TRIAL | 22 |
| 2.2 TRIAL OBJECTIVES..... | 22 |
| 2.3 BENEFIT - RISK ASSESSMENT..... | 22 |
| 2.3.1 Procedure-related risks | 23 |

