5.3.6 CF control during the trial

The safety of the subjects regarding CF during the trial will be assured by monitoring of FEV₁ and assessment of rescue and controller medication use and CF signs and symptoms. Subjects should be discontinued from the trial if, in the opinion of the Principle investigator, the subject is developing unstable CF, based on assessment of safety parameters described above.

The subjects will be instructed to make themselves available for the regular telephone monitoring for drug administration and their general well-being. Site staff will assess drug compliance, a subject's general well-being, rescue medication use and FEV₁ measurements via in-clinic visits, documented telephone monitoring and the AM3® device.

At home (ex-clinic) FEV₁ measurements:

At Day 1 for CF subjects, eligible subjects will receive hand-held electronic spirometers, [AM3®, eResearch Technology, Inc] from the site for their regular use during the entire study to monitor their FEV₁ whilst at home ([Flow Chart II](#)). In addition, CF subjects will perform an unsupervised manoeuvre on their AM3® device at screening (Day -7 to -3). The subject should perform three FEV₁ manoeuvres consistently, in a standing position with the AM3®. Instructions for use of the AM3® device will be provided to the subject.

All acceptable FEV₁ values are stored in the AM3® device with date and time of recording.

CF subjects:

Whilst the subject is at home (ex-clinic) morning and evening FEV₁ measurements will be performed on the AM3® prior to administration of study medication and background respiratory medication. In the morning, whilst the subject is at home (ex-clinic), the manoeuvre will be performed prior to or as part of the telephone visit under the supervision of the study site staff. If a relevant drop in FEV₁ compared to baseline (Day -7 to Day -3, morning, unsupervised AM3® manoeuvre) is observed the site staff will evaluate whether the subject needs to return to clinic prior to the morning visit.

During in clinic visits the AM3® data will be downloaded to a computer, the corresponding report printed and the data reviewed by the site in the morning on each visit day. The investigator will review/discuss the data with the subject and assesses the subject in regard to the data observed.

FEV₁ should also be measured at any time whenever the subject feels breathless or otherwise uncomfortable. The AM3® is primed to alarm following a 20% relative drop vs. baseline in

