FEV₁. Subjects must not take their trial medication dose, and must call the site if the device alarms.

FEV₁ data will be downloaded to a computer at each visit and printed out for review, signature and date by the investigator. Equipment will be withdrawn at end of study. Print-outs will be filed in the ISF.

Telephone visits:

During the treatment period when subjects are at home (ex-clinic), regular appointments for telephone calls between subject and investigator will be made. Calls will be made in the morning and evening for CF subjects. The following issues will be covered at each telephone visits in a sequential way:

1. Subjects will be reminded to take their correct trial medication dose.
2. Subjects will be questioned regarding general wellbeing.
3. Whether the subjects have performed a FEV₁ measurement with the AM3® that evening or that morning, if not subjects will need to perform the measurements during the course of the telephone calls. Site staff will ask whether the AM3 device has alarmed.
4. Subjects will be asked whether any AEs have occurred
5. Subjects will be reminded to conduct a FEV₁ reading and subsequently administer drug in the following evening or morning.

In any case of emergency during the trial the investigator must be available by phone for immediate assistance, therefore the subjects will be provided with 24-hour contact details.

Note: Documentation of AE if any (also if related due to i.e. a worsening of AE), change of any medication and intake of study medication have to be captured in the medical records and eCRF.

Details of any telephone visits as mentioned above, will be documented as source data in the subjects medical records.

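### The protocol uses one word, alarm, for the AM3 dose reminder and for the AM3 FEV1-drop alert, attaches opposite instructions to them, and describes nothing that tells them apart

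*Protocol*

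**What the plan says.** Protocol 4.3 (Treatment compliance) lists the means of supporting adherence in CF subjects at home. One is a telephone call morning and evening. Another is the home spirometer: the AM3 "device will alarm to remind the patient to take drug".

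Protocol 5.3.6 (CF control during the trial) gives the same device a second function. The AM3 "is primed to alarm following a 20% relative drop vs. baseline in" FEV1. The next sentence reads: "Subjects must not take their trial medication dose, and must call the site if the device alarms".

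The same section has home FEV1 measured on the AM3, morning and evening, "prior to administration of study medication and background respiratory medication". Its telephone script is to be followed in order. Item 1 is "Subjects will be reminded to take their correct trial medication dose". Item 3 checks that FEV1 has been measured and adds: "Site staff will ask whether the AM3 device has alarmed".

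On training, Flow Chart II footnote 17 provides for Respimat and AM3 "device training initially, then instruction (if required"), and 5.3.6 says that instructions for using the AM3 "device will be provided to the subject". Neither place says what subjects are told about alarms. The SAP does not mention the alarms.

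**The concern.** Taken at face value, an AM3 alarm means take the dose in one section, and withhold the dose and call the site in another. Two errors are possible. A subject who applies the 5.3.6 sentence to a reminder omits a scheduled dose and calls the site needlessly. A subject who has learned to treat the alarm as a reminder may dose after a real FEV1 fall, which 5.3.6 forbids. The telephone question does not name the alarm type either, so a yes or no answer may not show the site which event took place.

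At stake are the clarity of a stated home safety measure (section 2.3.2 lists AM3 monitoring among them) and, to a lesser extent, drug exposure and the count of completers.

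**Working it through.** The protocol gives no figure for alarms. The check is a comparison of text, followed by a count of the doses to which it applies.

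**1. The sentences side by side**
- 4.3: the event is that a dose is due; the action is to take drug.
- 5.3.6, first sentence: the event is a 20% relative FEV1 fall from baseline; no action is given in that sentence.
- 5.3.6, next sentence: the event is that the device alarms, with no type named; the action is not to dose and to call the site.
- 5.3.6, telephone item 3: the event is that the device has alarmed, with no type named; staff record the answer.

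**2. Is there a distinguishing feature?** Sections 4.3 and 5.3.6, the Flow Chart II footnotes and the SAP mention no separate tone, display or message.

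**3. Timing.** Home FEV1 comes before each dose on the same device, so a reminder and an FEV1-drop alert would fall around the same moment. In the call sequence, the prompt to dose (item 1) precedes the alarm question (item 3).

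**4. Doses affected.** Flow Chart II and section 4.1.4 give 27 administrations per period on the nominal schedule. The morning doses of Days 1, 7 and 14 are supervised in clinic. Home doses are:
- Day 1 evening: 1
- Days 2 to 6: 5 × 2 = 10
- Day 7 evening: 1
- Days 8 to 13: 6 × 2 = 12

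The sum is 1 + 10 + 1 + 12 = 24, and 24/27 = 88.9%. Table 4.1.4: 2 marks 27 as theoretical, without time windows. Assuming that dosing runs to the actual Day 14 visit (window -1/+3 days), home doses range from 24 - 2 = 22 of 25 (88.0%) to 24 + 6 = 30 of 33 (90.9%).

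**5. Effect of omitted doses on completion.** Section 3.3.5 counts a dosing period as completed only at 80 to 120% compliance. On 27 doses, 22/27 = 81.5% qualifies and 21/27 = 77.8% does not. Six omitted doses in one period would therefore make a subject a non-completer, against a target of at least 20 completers from 24 planned. This shows how many omissions would matter; it does not predict that they will occur.

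**6. What would catch an error**
- Morning: the manoeuvre is done before or during the call under site supervision, and staff evaluate a relevant fall from baseline. This does not depend on the alarm.
- Evening: staff ask whether FEV1 was measured and have it done during the call if not. The supervision described for mornings is not stated.
- Each home dose is captured by telephone, so an omitted dose is visible.
- AM3 values are stored with date and time, then downloaded and reviewed at clinic visits, which is after the event.

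**The case against.** The strongest reply is that the sentences are clear in context. The do-not-dose sentence directly follows the one on the 20% FEV1 fall, in a paragraph about measuring FEV1 when breathless. Few readers would apply it to a reminder described in a different section. This has force, and it is the likely intent. It does not help the subject or the telephone interviewer, who meet an alarm on a device rather than a sentence in a paragraph.

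A second reply is that AM3 training and device instructions may already separate the signals. That also stands as a possibility. A reader might infer that the device emits one identical signal for both purposes. The documents do not support that: they show a shared word and no described difference, and say nothing about the hardware.

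A third reply is that the other checks would expose a mistake. A reader might infer that neither error would be caught, and that is wrong: step 6 of the working lists several checks that do not rely on the alarm. What remains is thinner cover in the evening.

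Finally, a reader might describe the drug as having a known bronchoconstrictor liability and grade the point accordingly. Sections 1.2.1 and 2.3.2 report a preclinical signal, namely enhanced bronchoconstriction in guinea pigs challenged with acetylcholine or methacholine. Section 2.3.2 considers it not relevant in unchallenged volunteers and CF patients. It also reports no relevant adverse lung-function effect in healthy volunteers up to 1800 µg b.i.d., three times the CF dose (1800/600 = 3).

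**Conclusion.** The point holds as a conflict of wording in a safety instruction, and it should be fixed. Sections 4.3 and 5.3.6 use the same word for two AM3 signals with opposite consequences, and neither the do-not-dose sentence nor telephone item 3 says which is meant. The ambiguity applies to about nine in ten CF doses: 24 of 27 on the nominal schedule, or 22 of 25 to 30 of 33 if dosing follows the Day 14 window. Existing checks reduce the risk, least so for evening doses.

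The conclusion assumes that reminders are active at home doses, as 4.3 says, and that the training and device materials outside these documents do not settle the matter. If those materials already separate the signals, only the protocol wording needs correcting.

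Two further inferences go beyond the documents. One is a share of alarms that are mere reminders: it needs a rate of FEV1-drop alarms, which is not given, and it presumes that subjects would count a reminder when answering item 3. The other is harm to an endpoint or analysis: none is demonstrated.

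**What to change.** Reconcile 4.3 and 5.3.6:
- Name the dose reminder and the FEV1-drop alert separately, and use those names throughout.
- State in 5.3.6 which of the two the dosing instruction refers to.
- Confirm in the AM3 set-up and the subject instructions that the two can be told apart.
- Reword telephone item 3 to ask about the FEV1-drop alert specifically.

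What a subject does after an FEV1-drop alert is for the clinical team to decide; nothing is proposed here on that.

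The cost is protocol and subject-instruction wording and a check of the device configuration. No visit or measurement is added. No new eCRF field is needed, because the AM3 already stores acceptable FEV1 values with date and time.
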